5.3 Baseline Assessment

The baseline data, including demographics, injury mechanism, prehospital and ED hemodynamic variables, time to definitive care, mode of transport, presence of TBI, and fluids and blood products administered within the first 24 hours after injury will be obtained by the research coordinator as soon as feasible.

5.4 Clinical Data Collection

Because patient enrollment will occur at the scene of injury, there is no opportunity for baseline assessment of the patient by the clinical research coordinator; however, the ROC has an established infrastructure to facilitate obtaining all prehospital records including accurate time data from computer aided dispatch reports for all patients. Upon arrival to the hospital, a research coordinator will be available 24/7 at all sites. Direct bedside data collection will begin when the subject arrives in the ED and will continue until the patient receives the initial head CT scan and the hospital infusion is begun or for one hour, whichever occurs later. The time of arrival and time of initial head CT scan will be documented. GCS will be documented at these same time points. Data to be collected during this time period will include all fluid administered including hypertonic saline, all pharmacologic interventions including mannitol, all blood product transfusions, any procoagulant medications administered, history of current use of anticoagulant medications, life-saving interventions including intubation, initial clinical laboratory results, and surgical/neurosurgical procedures.

Data will be collected on a daily basis for the first 28 days of hospitalization or until discharge/death on all subjects who did not choose to discontinue further participation in the trial. Information collected will include demographics, injury scoring data, blood product transfusions, hemostatic medication administration, timing and dosing of DVT prophylaxis, GCS, intracranial pressure, cerebral perfusion pressure, neurosurgical interventions (including intracranial pressure monitor placement, brain tissue oxygen monitor placement, microdialysis catheter placement, ventriculostomy, and decompressive craniotomy/craniectomy), timing of clinically indicated repeat head CT scan (including GCS at the time of repeat CT), other surgical procedures, vital signs, and routine daily lab results. In those institutions where CT is repeated in all patients with intracranial bleeding by protocol, the 2nd CT will be performed 6 hours after the first. Complications recorded will include the following: thromboembolic complications (stroke, DVT, PE, MI) including results of thromboembolic screening procedures (including MRI, duplex ultrasound, PE protocol CT scans, electrocardiograms [EKGs]), results of electroencephalograms (EEG) evaluating seizures, results of transcranial doppler evaluating vasospasm, multiple organ failure (Multiple Organ Dysfunction Score), acute

respiratory distress syndrome (ARDS - based on the Berlin definition), transfusion related ARDS, acute kidney injury, diabetes insipidus, hyper- and hyponatremia, infections, and sepsis. A pre-specified list of clinically indicated available lab results will be recorded and commonly include blood alcohol level, complete blood count (CBC) with platelets, electrolyte panel, coagulation tests (aPTT/ INR), fibrinogen, troponin, lactate, arterial and venous blood gas, and urinalysis. In addition to the information collected daily, the final discharge diagnosis, and discharge destination (home, long-term acute care hospital, skilled facility, death) will be recorded. A discharge GOS-E and DRS as well as a Neurologic Assessment: Symptoms and Signs Present will be obtained at the time the subject is discharged from the hospital. A 6-month GOS-E and DRS as well as a Neurologic Assessment: Symptoms and Signs Present will be obtained at 6 months after injury. (See Appendix 3 GOS, GOSE, DRS and Neurological Assessment: Symptoms and Signs Present)

5.5 Research Laboratory Data Collection

Blood samples will be collected during the first 48 hours after admission from all subjects who have not withdrawn participation in the trial. Blood samples will be collected upon arrival in the ED (time 0) for all enrolled/randomized subjects and at 6, 12, 24, and 48 hours (or discharge from hospital – whichever occurs first). Studies to be performed at these time points include measures of fibrinolytic pathway activity. Kaolin activated TEG will also be performed on citrated blood samples at these time points for functional analysis of coagulation. Available data from these studies will be for research use only and will not be available for clinical decision making. In addition to the studies listed above, blood will be collected and stored at the same time points for inflammatory marker analysis for which additional funding will be sought. Blood will be stored for future testing only related to TBI, intracranial hemorrhage, fibrinolytic pathway mediators and other coagulation factors. The specimens will be stored for future use in a de-identifiable manner such that the patient's identity will not be able to be ascertained. We chose these 5 time points to provide a broad temporal survey of coagulation changes after TBI weighted toward early sampling to fully characterize the early phase of coagulopathy. Later sampling at 24 and 48 hours will allow characterization of the transition from a hypocoagulable to a hypercoagulable state and full examination of the effect of the intervention on coagulation and inflammation after TBI. All attempts will be made to obtain study samples at the pre-specified time intervals and samples at times 0, 6, and 12 hours must be collected within +/- 30 minutes. Sampling at 24 and 48 hours will be collected within +/- 2 hours. In the event that samples cannot be collected in this time frame, documentation regarding the reason will be noted on the data collection forms. Up to 23 ml of blood will be collected in addition to the clinical sampling at each time point. Samples will be collected by the clinical person responsible for implementing physician orders for laboratory testing. The clinical research staff will then be responsible for processing and shipping at each site. All samples drawn for research purposes will be identified by the study number, the site identification number and date/time of collection. No personal identifying information will be included on the samples processed for research purposes. Assays that require immediate processing (TEG and CBC) will be performed at each study site by trained personnel. Other samples will be spun, aliquotted, frozen at -80°C, bar coded, and batch shipped by the clinical research staff to the Trauma Research Institute of Oregon, Oregon Health & Science University. The research laboratory data will be entered into a web based relational database created for the lab measurement component of this trial.

5.6 Image Collection and Processing

To reduce observer variation, we will perform a central review of all CT scans, a process that is considered essential in multicenter trials utilizing imaging studies. Each site will obtain digital images of all head CT scans obtained during the first 28 days of the subject's initial hospitalization in Digital Imaging and Communication in Medicine (DICOM) format, which will be made available electronically by remote access, on a storage device, or via a secured file transfer protocol (FTP) upload site to OHSU CCC within two weeks of a subject's discharge from the enrolling hospital. All MRI scans will be uploaded via the same mechanism to the OHSU image repository. All images will be stored in a de-identified manner. Head CT scans will be reviewed centrally at OHSU under the direction of a neuroradiologist who will be blinded to the treatment group assignment. A technician will be trained to utilize software designed to obtain computerized measurements of ICH volumes. The central neuroradiologist will audit 10% of scans to verify that accurate and consistent measurements are obtained. MRI and CT scans will be maintained in the imaging repository for future

analyses that may include computer-aided lesion analysis and/or regional brain volumetrics.

5.7 Concurrent Care

Prehospital care: there is significant variability in EMS systems resulting in difficulties associated with attempting to standardize care. Prehospital airway, fluid and blood product administration will not be standardized; however, detailed prehospital data will be collected to determine if there are potential differences in important prognostic treatment variables among different study sites. We will encourage the study drug to be administered as soon as possible after life-saving interventions are performed and prior to administration of blood products; however, there may be circumstances where this is not feasible.

In-hospital care: in order to minimize variability in subsequent management of TBI, all sites will have 24 hour neurosurgical capability and will encourage the implementation of management guidelines set forth by the Brain Trauma Foundation that are supported by evidence based medicine.⁹ Additionally, evidence-based guidelines and protocols for critical care management will be encouraged and monitored and will include the following: management of severe TBI, early use of head CT with liberal use of repeat head CT for patients with ICH, massive transfusion protocol, transfusion guidelines for trauma patients, early detection and treatment of myocardial infarction and stroke, mechanical ventilation protocol, sedation/analgesia protocol for mechanical ventilation, early nutritional support protocol, glucose control in the ICU, diagnosis & treatment of ventilator associated pneumonia, adherence to surviving sepsis campaign guidelines, and venous thromboembolism surveillance and prophylaxis protocol for prevention. In cases where a repeat CT is clinically indicated, it will be performed at approximately 6 hours.

5.8 Early Termination of Study Drug

When EMS personnel open the blinded study drug kit, the patient is enrolled and randomized and will be included in the primary statistical analysis if the study drug is connected to the patient's IV access. The study drug will be terminated by EMS or by hospital providers for any of the reasons below.

- Prehospital provider suspects the patient has developed a thrombotic event (MI, ischemic stroke,) or seizure activity OR after hospital arrival the patient develops a thrombotic event (MI, PE, ischemic stroke, or symptomatic DVT) or seizure activity
- The patient requires cardiopulmonary resuscitation (CPR)
- The patient, patient's family member or legally authorized representative (LAR) withdraws from the study
- The patient is discovered to be pregnant
- A serum creatinine > 2.0 mg/dL is obtained
- The patient requires administration of Factor IX Complex concentrates or Anti-inhibitor Coagulant concentrates
- The patient is discharged from the hospital prior to completion of the 8 hour infusion

6. Study Outcome Measures

6.1 Primary Outcome Measure: 6 Month Neurologic Outcome

Two National Institutes of Health (NIH) consensus conferences have addressed clinical trial design for interventions designed to impact outcome from TBI.^{81,82} The first emphasized the importance of assessing long term outcome following brain injury and recommended use of the Glasgow Outcome Score (GOS) for subjects with severe brain injury (GCS ≤ 8) and the DRS for subjects with less severe brain injury (GCS 8-13).⁸¹ A subsequent conference recommended a 6 month follow-up utilizing outcomes that are "measurable, standardized, and relevant to lifestyle."⁸² Specifically they recommended the use of the GOS-E. The rationale for this recommendation is that the GOS-E provides a better distinction between levels of disability, particularly

within the severe disability groups, while the GOS combines a wider range of disability into one category. Furthermore, combining the GOS-E with the DRS increases the ability to detect improvement following TBI.^{83,84,85,86}

Detailed neurocognitive, behavioral, and psychological testing has been advocated for full assessment of neurologic outcome following TBI. This approach requires that the patient return to the trauma center for intensive testing and requires extensive training for those administering the assessments. This approach has not been directly compared against the most widely used measures of GOS-E and DRS. Furthermore, recent experience with this approach in a TBI outcome study demonstrated a 50% rate of refusal by the patients to return for this detailed testing.⁸⁷ Thus, application of these outcome assessments in this trial would exceed available resources, increase the risk of poor inter-rater reliability, and result in inadequate follow-up rates for subsequent analysis.

Extended Glasgow Outcome Score: The GOS was first proposed by Jennet and Bond in 1975.⁸⁸ It is a simple four-point scale based on the degree of patient disability. It has been widely adopted based on its simplicity and high inter-rater reliability.^{89,90,91} An Extended Glasgow Outcome Score (GOS-E) was subsequently developed which further subdivides the categories of severe and moderate disability and good recovery.⁹² Structured telephone interviews have been developed and validated for both the GOS and GOS-E and these questions will be incorporated into our follow-up survey.^{86,92} For each level of function, the baseline function prior to injury is assessed to ensure that the deficit can be attributed to the event. The GOS and GOS-E have been shown to correlate well with several other outcome measurements after TBI including neuropsychological and cognitive testing, the DRS, and measures of perception of health (SF-36).^{85,92,93} The GOS-E will be assessed at discharge and at 6 months after injury. The GOS-E measured at 6 months will be the primary outcome for this trial.

Outcome assessment: Outcome assessment will be performed by telephone survey that includes the key components of the GOS-E and will be administered to patients or their caregivers at the time of discharge for baseline assessment and at 6 months after injury. Attempts will be made to contact the patient directly; however, for patients who are severely disabled, information will be obtained from the primary caregiver. Reliability will be assessed and if the patient is determined to be unreliable, a caregiver will be sought to complete the survey. Previous studies demonstrate that caregiver assessment is a valid means of assessing these outcome parameters.^{92,103,94} Previous follow-up in the TBI population demonstrate variable success in achieving adequate response rates ranging from 73% to 99% follow-up at 6 months.^{95,96,97} The ROC DCC has extensive experience with long-term outcome assessment in both TBI and non-TBI populations. In a large multi-institutional study evaluating prehospital hypertonic saline administration in TBI conducted by the ROC, an 85% response rate was achieved.⁹⁸ We will utilize this model that includes a detailed contact list collected from the patient or family and friends prior to discharge and a log for tracking follow-up attempts by the study coordinators. The Public Access Defibrillator trial used a similar follow-up method and although not a trauma trial, this model resulted in 100% follow-up for the primary endpoint.⁹⁹ In addition, telephone contact at one month post discharge will be initiated to establish a relationship and commitment for the 6 month interview.

6.2 Secondary Outcome Measures

- *Clinical outcomes:* Observed volume (absolute and relative) of ICH progression, proportion of patients who develop observed ICH progression (as defined below), Rotterdam and Marshall CT classification scores, DRS at discharge and 6 months, GOS-E at discharge, 28-day survival, frequency of neurosurgical interventions, and ventilator-free, ICU-free, and hospital-free days.
- *Safety outcomes:* Development of seizures, cerebral ischemic events, MI, DVT, PE
- *Mechanistic outcomes:* Alterations in fibrinolysis based on fibrinolytic pathway mediators and degree of clot lysis based on kaolin activated TEG and defined as LY30 or the per cent lysis that occurs 30 minutes after maximum amplitude (MA) is achieved.

ICH progression is associated with an increased need for neurosurgical intervention and is independently associated with a 5-fold increased mortality in patients with TBI.²¹ If seizures or other adverse outcomes are found in this trial, it will be important to balance the potential benefit in reduction of ICH progression with the risk of an adverse outcome to determine the overall impact of TXA. All clinically indicated head CT scans obtained during the initial hospitalization or within the first 28 days will be assessed for ICH. All cerebral and carotid/vertebrobasilar CT and standard angiograms will be assessed for blunt cerebrovascular injury. Parenchymal, subdural and epidural hemorrhage volumes will be measured and quantified using volumetric software and verified by manual calculations based on the previously validated ABC/2 technique as needed.¹⁰⁰ Ten percent of all scans will be audited by a single neuroradiologist for accuracy. Each case in which a disparity is detected will be discussed with the neuroradiologist resulting in review of additional cases and retraining of the technologist as necessary. Subarachnoid hemorrhage (SAH) will be categorized as ≤ 5 mm or > 5 mm. Intraventricular hemorrhage (IVH) will be visually assessed as present or absent on all scans with progression determined by direct comparison of studies by a neuroradiologist. New focal ischemic lesions will be defined as an area of focal low attenuation in a distribution indicating an arterial ischemic cause rather than a traumatic contusion and will be rated using a validated scale for ischemic stroke.⁶⁰ Mass effect will be defined as sulcal effacement, ventricular effacement, uncal herniation, cistern compression, and midline shift. The following outcome measures will be recorded: the difference in the total hemorrhage volume across scans, determination of significant hemorrhage progression between scans defined as greater than a 33% increase, presence of a new ICH, worsening of SAH grade, worsening IVH or mass effect, and the development of new focal cerebral ischemic lesions. We have chosen to define progression of subdural, epidural and intraparenchymal hemorrhages as an increase of $> 33\%$ over baseline based on the description by Brott et al.¹⁰¹ This number is based on the following: a 33% change in the volume of a sphere corresponds to a 10% increase in diameter, which is considered a clear difference to the naked eye of a physician viewing serial CT scans of a patient with an ICH.¹⁰¹ Thus, this difference can be assessed clinically without using volumetric software applications. Second, previous experience suggests variability in measurement of lesions may occur due to variation in patient positioning and angles of the CT slice images rather than to an actual increase in hemorrhage volume, especially for small hemorrhages. Thus, by using an increase of $> 33\%$, our CT definition of intraparenchymal, subdural, and epidural hemorrhage progression is conservative and is more likely to represent true hemorrhage growth as opposed to variability in CT imaging.¹⁰¹ All MRI scans during the initial hospital stay performed as part of routine clinical care will be uploaded with CT imagines to the imaging repository for future analyses that may include computer-aided lesion analysis and/or regional brain volumetrics.

The DRS is designed to classify patients based on their degree of function after brain injury. The DRS consists of 8 items that fall into 4 categories: a) arousability, awareness and responsivity, b) cognitive ability for self-care activities, c) dependence on others, and 3) psychosocial adaptability.¹⁰² The DRS has been reported to be more sensitive than the GOS-E for changes in function over the first year following injury.¹⁰³ This may be particularly important for patients with moderate TBI. In this trial we will be enrolling patients with both moderate and severe brain injury. The DRS will be administered to patients or their caregivers at the time of discharge for baseline assessment and at 6 months after injury by telephone survey along with the GOS-E.

Laboratory assessment of coagulation will include fibrinolytic pathway mediators. These mediators are important in the fibrinolytic pathway and will provide insight into the mechanism underlying an observed treatment effect. TEG will be performed at serial time points as a viscoelastic measure of coagulation and fibrinolysis.

7. Sample Size for the Primary Outcome

The primary outcome is favorable neurologic function at 6 months after injury based on the GOS-E > 4 . Good outcome corresponds to either moderate disability or good recovery (GOS-E > 4), while poor outcome corresponds to death, vegetative state, or severe disability (GOS-E ≤ 4). The total sample size in the primary analysis population will be 963 (321 per group). The sample will include randomized patients for whom the

treatment is started (modified intention to treat population). Power computations were based on a comparison of binomial probabilities with assumed variance larger than given by the binomial distribution; the hypothesized additional variance would be contributed by the multiple imputation of outcomes for subjects with missing outcome data. Based on results from the TBI cohort in the ROC hypertonic saline trial,⁹⁸ we assumed that 40% of subjects treated only with placebo would have a poor neurologic outcome (GOSE \leq 4) at 6 months, that 15% of subjects would be missing 6-month outcome data, and that the per-subject additional variance contributed by the multiple imputation of the outcomes was 10^{-6} . Under these assumptions, our sample size will allow for 80% power to detect a 7.1% absolute increase in a favorable GOS-E (> 4) at six months post injury comparing the combined TXA treatment groups to placebo, using a one-sided, level 0.1 test. Similarly, in testing for harm, this sample size will allow for 80% power to detect an absolute decrease of 9.5% in the proportion of patients with a favorable long-term neurologic outcome, using a one-sided, level 0.025 test.

8. Analysis Plan

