Sample size: The total sample size in the primary analysis population is 963 (321 per group), which will allow for 80% power to detect a 7.1% absolute increase in the proportion of patients with a favorable long-term neurological outcome as determined by the GOS-E 6 months after injury comparing patients who receive TXA to patients who receive placebo, using a one-sided, level 0.1 test. It will allow for 80% power to detect an absolute decrease of 9.5% in the proportion of patients with a favorable long-term neurologic outcome comparing patients who receive TXA to patients who receive placebo, using a one-sided, level 0.025 test.

Statistical analysis of primary hypothesis: Modified intention-to-treat analysis using logistic regression to test for association and estimate the strength of the association of treatment group with a favorable 6-month outcome (defined as a GOS-E > 4), after adjustment for study site.

Human subjects protection: This study qualifies for the exception from informed consent (EFIC) required for emergency research outlined in FDA regulation 21CFR50.24. EFIC applies because of life-threatening situation, intervention must be administered before consent is feasible, no reasonable way to identify prospectively individuals at risk, patients have the prospect of benefit from the treatment, and the research could not practically be carried out without the waiver of consent.

1. Overview

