8.4 Plan for Missing Data

All possible efforts will be made to avoid missing outcome data. These include collecting detailed contact information from a variety of different sources prior to hospital discharge (address, email, other family members, friends, physicians), contacting the patient/family within one month of discharge to establish a continued relationship, and integrating TXA follow-up with other medical follow-up (e.g. clinic, physical therapy). For the primary analyses, any missing outcomes will most likely be due to study patients withdrawing from participation in post-discharge follow-up or dropping-out. Neurological status at discharge is highly correlated with neurological status at 6 months.¹⁰⁷ Specifically, we anticipate that patients who have a “good outcome” at discharge tend to improve and not get worse and those that have a “poor outcome” tend to remain at the same status or improve. In primary analyses, multiple imputation methods will be used to account for missing outcome data.^{108,109,110} Sensitivity analyses will consider modified worst-case (last observed GOS-E score minus 1) for missing outcomes in all treatment arms, and a modified best-case (last observed GOS-E score plus 1) for missing outcomes in all treatment arms.

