8.5 Sequential Monitoring Plan

Because of the fear that selection criteria based only on field data may potentially include subjects who would not be able to benefit from TXA treatment, one formal futility analysis will be conducted based on outcome data from the first 200 subjects in the analysis population and reported to the ROC DSMB, using a Wang-Tsiatis boundary.¹¹¹ The early stopping for futility is described in Table 1. The futility stopping rule would categorize results at the first analysis as futile if the observed crude difference in probabilities of a bad neurologic outcomes (GOSE < 5 at 6 months post injury) corresponded to an absolute increase of 6.8%. As can be seen from the 95% confidence interval, this futility decision would nearly rule out the hypothesized improvement of 7.1%.

Table 1: Protocol Stopping Rule							
		Futility Boundary			Efficacy Boundary		
	N accrued	Z	Crude Diff	Est (95% CI; one-sided P)	Z	Crude Diff	Est (95% CI; one-sided P)
First	200	0.955	.068	-.047 (-.072, .125); P = .82	NA	NA	NA
Second	963	-1.266	-.042	-.048(-.109, .022); P = .10	-1.266	-.042	-.048(-.109, .022); P = .10

Table 2 presents the probability of declaring superiority, futility or inferiority for selected hypothesized values of the true treatment effect. The incorporation of the futility stopping rule affects the power of the study to detect benefit of TXA very little, moving the minimal absolute treatment difference that can be detected with 80% power from -0.070 to -0.071.

Treatment Diff	Pr[superior] (power)	Pr[Futile]	Pr[inferior]
-.071	.80	.20	0
-.05	.59	.41	0
-.03	.35	.64	0
-.02	.25	.75	.01
-.01	.16	.82	.01
0	.10	.88	.02
.01	.06	.90	.05
.02	.03	.89	.09
.05	0	.68	.31
.10	0	.16	.84

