8.8 Roles and Responsibilities of the Medical Monitor

An independent medical monitor will review all unexpected problems involving risk to subjects or others, SAEs and all deaths related to TBI and provide an unbiased written report of the events. At a minimum, the medical monitor must comment on the outcomes of the event or problem and in case of an SAE or TBI-related death, comment on the relationship to participation in the trial. Because a moderate number of deaths (approximately 15% based on Trauma Epistry Registry data for patients with $GCS \leq 12$)⁷ are expected due to the presence of moderate and severe TBI in the subjects enrolled prior to the intervention, individual reports to the ROC DSMB will be aggregated and reported on a timely schedule acceptable to the ROC DSMB. If the death is considered unexpected and is either suspected or probably due to treatment, this event will be promptly reported to the medical monitor and the ROC DSMB. The medical monitor must also indicate whether he/she concurs with the details of the report provided by the principal investigator. Reports for serious adverse events determined by either the investigator or medical monitor to be possibly or definitely related to participation must be promptly reported per FDA, DoD and/or Health Canada guidelines.

[name] is the independent medical monitor for this study. He has committed to comply with the following statements:

The monitor:

- Is independent of the research team.
- Possesses sufficient educational and professional experience to serve as a subject advocate.
- Will promptly report discrepancies or problems to the IRB.
- Has the authority to stop the research in progress, remove individual subjects from the research, and take whatever steps are necessary to protect the safety and well-being of the subjects until the IRB can assess the monitor's report.

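### The stated 80% power is said to allow for 15% missing 6-month outcomes, but the assumed imputation variance is effectively zero, so it is complete-data power

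*Combined protocol and SAP*

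**What the plan says.** Section 7 (Sample Size for the Primary Outcome) describes the variance model as follows: "Power computations were based on a comparison of binomial probabilities with assumed variance larger than given by the binomial distribution". The excess is attributed to multiple imputation of missing outcomes. Citing the TBI cohort of the earlier hypertonic saline trial, it assumes a 40% poor-outcome rate on placebo, 15% missing 6-month outcomes, and that "the per-subject additional variance contributed by the multiple imputation of the outcomes was 10^{-6"}. It then concludes: "Under these assumptions, our sample size will allow for 80% power to detect a 7.1% absolute increase in a favorable GOS-E", at one-sided level 0.1, with 80% power for a 9.5-point decrease at one-sided level 0.025.

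The Summary repeats the claim without the assumptions: "The total sample size in the primary analysis population is 963 (321 per group), which will allow for 80% power to detect a 7.1% absolute". Section 8.5 describes the futility look as "moving the minimal absolute treatment difference that can be detected with 80% power from -0.070 to -0.071", and its Tables 1 and 2 give boundaries and operating characteristics.

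On predicting missing outcomes, Section 5.4 collects "A discharge GOS-E and DRS as well as a Neurologic Assessment" at hospital discharge, and Section 8.4 states: "Neurological status at discharge is highly correlated with neurological status at 6 months". No correlation or fraction of missing information is given.

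**The concern.** A reader of Section 7 will take it that 15% missing outcomes are already built into the 80% power for both benefit and harm. That holds only if the extra variance is large enough to matter. An addition of one millionth to a per-subject variance of about one quarter amounts to assuming that imputation recovers every missing outcome almost perfectly. The text does not say what the term is added to, over how many subjects it applies, or how it was obtained.

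At stake is whether the headline power and Tables 1 and 2 describe the trial as planned or a trial with no missing outcomes. The harm test deserves particular care because patients are enrolled under exception from informed consent.

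**Working it through.** **Inputs.** 321 placebo and 642 combined TXA; 60% favorable on placebo; one-sided 0.1 for benefit and 0.025 for harm; 15% missing; extra variance 10⁻⁶ (all Section 7). Futility bound Z = 0.955 at 200 subjects and final bound 1.266 at 963 (Table 1).

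**Formula.** SE = √[pT(1−pT)/642 + 0.24/321], divided by √(information fraction). Power = Φ(|difference|/SE − z), with z = 1.2816 or 1.9600. Variances are unpooled unless stated.

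**1. Reproduce the plan's figures with complete data.**
- At +7.1 points: SE = √(0.671×0.329/642 + 0.24/321) = 0.0330; power 80.7%. The 80%-power difference is 0.0702 (plan: 0.070).
- With the futility look: power 80.0% at 7.1 points; 80%-power difference 0.0710 (plan: 0.071).
- At −9.5 points: power 80.4%; 80%-power difference 0.0945, or 0.0955 with pooled SE (plan: 9.5 points).
- Table 1, final row: implied SE = 0.042/1.266 = 0.0332 (0.0328–0.0336 allowing for rounding). Complete data give 0.0330–0.0335; a 15% information loss gives 0.0358–0.0363.
- Table 2: every superiority cell (with the look) and every inferiority cell is within 0.01 of complete data. At 15% loss the largest gaps are 0.052 and 0.059. For example, superiority at −0.071 would be 0.75, not 0.80, and inferiority at +0.10 would be 0.78, not 0.84.

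**2. Effect of the 10⁻⁶ term.**
- Added to each subject's variance: the benefit difference moves from 0.0701602 to 0.0701604.
- Summed over the imputed subjects (0.15 × 963 = 144.45) and added to the variance of the difference: 1.44×10⁻⁴ on top of 1.09×10⁻³ gives 77.0% for benefit and 75.6% for harm. This reading has an effect, but it does not reproduce the stated 80%.
- If the exponent were misread from the PDF and 10⁻³ was meant: benefit difference 0.0703, power 80.6%, still essentially complete data.

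**3. Size of term a real loss would need.** Spread over all subjects, a loss L corresponds to 0.24·L/(1−L): 0.0126 at 5%, 0.0195 at 7.5% and 0.0424 at 15%. The 5% figure is more than 10,000 times the stated value.

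**4. Power under assumed information loss** (unpooled SE, no futility look):

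| Loss | Benefit power at 7.1 points | 80%-power benefit | Harm power at 9.5 points | 80%-power harm |
|---|---|---|---|---|
| 0% | 80.7% | 7.02 | 80.4% | 9.45 |
| 5% | 79.2% | 7.20 | 78.4% | 9.69 |
| 7.5% | 78.4% | 7.29 | 77.3% | 9.82 |
| 15% | 75.8% | 7.60 | 73.8% | 10.25 |

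**5. Where the loss might lie** (my assumptions, not document figures).
- Simulation with 15% missing completely at random, imputing from a binary discharge status: when that status agrees with the 6-month outcome 95%, 90% or 80% of the time, the fraction of missing information is about 0.04, 0.07 and 0.11. It is about 0.15 if discharge status is uninformative.
- If 15% are known deaths, all missing outcomes fall at random among survivors and no other predictor is used: with q = 0.6/0.85, loss = 1 − 0.24/[0.85q(1−q)/(1−0.15/0.85) + 0.15(0.85)q²] = 13.6% (power 76% and 74%).
- If two equal strata have 70% and 50% favorable and all missing outcomes fall in the second: loss = 1 − 0.24/[0.5(0.21) + 0.5(0.25)/0.7 + 0.25(0.2)²] = 18% (power 75% and 72%). So 15% is not a strict ceiling.

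**6. No allowance elsewhere.** The sample size justification in Appendix 3 explains the step from 1002 to 963 by the 4% of kits expected to be opened but not given (1002 × 0.96 = 962). It does not cover missing outcomes.

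**The case against.** Five points can be made for the plan.

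- *The assumption is disclosed and tied to earlier data.* Section 7 prints both the 15% and the 10⁻⁶, and its wording can be read as drawing both from the hypertonic saline trial. The 80% follows from the literal inputs, so there is no arithmetic slip. This stands, but attribution neither defines the term nor shows how it was derived.
- *The per-subject equivalents depend on scaling.* Spread over only the 15% imputed, they become about 0.084 (5% loss) and 0.28 (15% loss). True, and this shows why the term needs a definition; it widens the gap.
- *The tables are not exact evidence.* The interim row of Table 1 implies SE = 0.068/0.955 = 0.0712, while complete data at 200 subjects give about 0.0725–0.0739. That row does not fit and its estimate and interval were not reproduced, so I do not rely on it. Its misfit is towards less variance than complete data, so it offers no sign of a missing-data allowance.
- *The real loss is probably small.* Discharge GOS-E is collected and described as strongly related to the 6-month outcome. Deaths count as poor outcomes and Section 8.8 expects a substantial share: "Because a moderate number of deaths (approximately 15% based on Trauma Epistry Registry data for patients with" GCS of 12 or less. Appendix 1 retains vital status at discharge even after withdrawal. This stands: with a strong predictor the shortfall could be within about two percentage points.
- *The two analytic cases in step 5 leave out discharge GOS-E.* Also true. They show only that the loss need not be negligible or capped at 15%, and they are not forecasts.

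**Conclusion.** The point holds. The 80% figures, the detectable differences, the final row of Table 1 and the superiority and inferiority columns of Table 2 are those of 963 complete outcomes, so the stated allowance for 15% missing data has no numerical effect. That conclusion rests on reproducing the printed results and does not depend on how the exponent is read.

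The size of the shortfall is not established by the documents. On the basis in the table above, it runs from about one to two points of power at 5% information loss to about five (benefit) and seven (harm) at 15%. It may well be at the lower end if discharge GOS-E predicts strongly. The design is not undermined, but the headline claim is wrong as written and should be corrected.

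**What to change.** 1. Define the imputation variance term: what it is added to, and over how many subjects.
2. Replace it with a fraction of missing information estimated from the hypertonic saline trial data that Section 7 already cites, with discharge GOS-E and known deaths in the imputation model.
3. Recompute the power and detectable differences in the Summary, Section 7 and Tables 1 and 2, using the sponsor's own SE formula and one stated basis for the futility look.

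Alternatively, state in one sentence that the 80% figures assume complete 6-month outcomes, and give the power for benefit and harm under plausible information loss.

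The cost is slightly less favorable restated figures, or one added sentence. No patients are added, and the test, alpha and estimand stay as they are.
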